4.3. PRE-CLINICAL/CLINICAL DATA

This highly variable pathophysiology of pre-school wheeze is reflected in the response to treatment, making the determination of phenotype much more than a matter of academic importance. In the first serious attempt to apply personalised medicine to this group of patients, the INFANT study investigators used a three way crossover design to compare the differential response to therapy with intermittent ICS, regular ICS and montelukast in 300 children (15). Sixty improved spontaneously over the duration of the study. Atopic sensitisation predicted a good response to ICS, shown by reduced numbers of attacks of wheeze and better control of chronic symptoms. In a retrospective analysis, an elevated blood eosinophil count and even better, a combination of positive SPTs and peripheral blood eosinophils $>300/\mu\text{l}$ were the best predictors of a good response to regular ICS. Leukotriene receptor antagonists were not beneficial in any group. Those with no positive SPTs or elevated eosinophil count rarely had acute attacks of wheeze. These findings, especially the predictive power of blood eosinophil count, need to be tested prospectively in primary care, the setting in which most of these children are treated, in a large prospective randomised controlled trial. Prior to this, pilot data to inform power calculations, and the feasibility and

acceptability of this approach needs to be determined. Additionally, although FeNO in preschool children is not well standardized there is one study which proposed FeNO values ≥ 10 ppb to be predictive of eosinophil inflammation in preschool children (16).

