5. STUDY'S AIM AND OBJECTIVES

AIM: To obtain pilot data to test the hypothesis that aeroallergen sensitisation (confirmed by a wheal formation with a diameter ≥ 3 mm after a skin prick test is performed), FeNO (offline method) ≥ 10 ppb and a peripheral blood eosinophil count $\geq 300/\mu\text{l}$, alone or in combination, can predict future wheezing exacerbations in preschool children as well as response to treatment with inhaled corticosteroids, as a preliminary to a large, randomised controlled trial. Also, that these tests are acceptable to families.

OBJECTIVES:

- To recruit 100 preschool children with a history of wheeze, aged one to five years old, and determine atopic status, peripheral blood eosinophil count (point of care test) and FeNO (offline method).
- To evaluate the feasibility and acceptability of these tests
- To categorize the children according to the biomarkers tested and assess whether any or all, alone or in combination, predict future wheezing exacerbations as well as determine the clinical outcome over one year
- To obtain parents' and doctors' insights into whether the biomarkers mentioned above could be used in a future intervention study.

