6. STUDY DESIGN

This is a pragmatic, observational study involving preschool children with wheeze aged one to five years old. All treatment and routine monitoring decisions will be at the discretion of their treating general practitioner (GP) or paediatrician (as per usual clinical practice), blinded to the study measurements. After clinical consultation and following submission of the electronic informed consent through the Qualtrics® platform (offered by Imperial College London), the parent/carer will be asked to give the contact details of the child's GP or paediatrician, who will be informed about child's participation in this study through a letter sent to his/her email along with the patient information sheet. The parent carer will be then shown a standard video questionnaire and will be asked to identify what respiratory sounds their children have been making. The child will be booked for the three biomarker tests [atopic sensitisation, blood eosinophil count and FeNO (off-line method)]. The tests will be carried out once and at a time of clinical stability. In this visit, a sample of the child's exhaled tidal breath will be collected in a suitable bag in duplicate for offline measurement of FeNO later on with chemiluminescence. Skin prick tests will be performed to: (a) house dust mite, (b) grass pollen, (c) tree pollen, (d) cat hair(e) dog hair, as well as normal saline and histamine and these will be applied on either the child's back, leg or arm. If the child has been prescribed antihistamines, we will ask for these to be withheld for 72 hours prior to skin prick testing. FeNO values (offline method) ≥ 10 ppb will indicate Type 2 inflammation and wheal diameter, measured with a specialised skin prick test ruler, ≥ 3 mm will indicate sensitisation to the applied aeroallergen. In addition, skin prick tests will allow the assessment of which aeroallergen is the most useful predictor of outcomes in preschool children. Finally, the peripheral blood eosinophil count will be measured from a finger prick blood sample, using the Haemocue machine, allowing a result in approximately 2 minutes. Values ≥ 300 cells/ μ l indicate Type 2 inflammation. All tests will normally take no more than one hour.

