In the event that a child has had their ICS treatment discontinued, we will record whether this was because the treatment was ineffective (treatment failure) or if the child was so well that the family or GP did not wish to continue (treatment success or spontaneous improvement). If an additional medication is prescribed, or the child is referred to secondary care, this will be considered as treatment failure. When the study ends, participants' parents/carers will be invited to a face-to-face focus group interview, or a one-to-one interviews, or remotely through Microsoft Teams, depending on their availability at the end of the study period. The focus group and one to one interviews will utilise a semi structured questionnaire, to provide qualitative feedback on the acceptability of the 3 biomarker tests. In addition, a separate focus group for doctors and nurses will be conducted to assess the feasibility of the 3 biomarker tests being used in clinical practice. They will be given all the information regarding the study as well as the study's patient information sheet. Those agreeing to take part, will sign a consent form. They will be attending either a face-to-face focus group interview, or a one-to-one interview, or remotely through Microsoft Teams, depending on their availability. A semi structured questionnaire will be utilised. Where possible a second independent researcher will sit in the focus groups discussion and interviews to ensure there is no bias. The conversations from the focus group and one to one interviews will be transcribed and coded into themes. We will utilise an external company for transcribing the conversations called 1st Class. <https://www.1stclass.uk.com/>

The focus group and one to one interviews will be audio recorded, transcribed and put into themes to conduct an inductive thematic analysis. 25% of the transcripts will be

double coded by an independent researcher, experienced in qualitative research to ensure that the correct themes have been used and to ensure that there is no bias. The focus group and one to one interviews will be used to assess the acceptability and feasibility of measuring biomarkers in primary care and using them to help determine management of preschool wheeze.

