7.2. INCLUSION AND EXCLUSION CRITERIA

7.2.1. CHILDREN

INCLUSION CRITERIA	EXCLUSION CRITERIA

1. Patients aged one to five years old presenting to primary care or to the emergency department or to secondary care (e.g., outpatients) or identified from primary care records and have been diagnosed with wheezing by their GP or paediatrician who has decided to prescribe any bronchodilator, ICS or montelukast on clinical grounds
	
1. Inability to understand and cooperate with study procedures
 
2. Significant co-morbidity (respiratory or otherwise), for example cystic fibrosis (excluding atopic disorders such as eczema, allergic rhinitis and food allergy)
 
3. Withholding or withdrawal of informed consent

2. Parents/Carers able to understand and familiarize themselves with the study and are willing to provide informed consent
	
4. Severe procedural anxiety (needle phobia)
 
5. Child is already enrolled in another study involving investigational medicinal product (CTIMP)
 
6. History of near-fatal asthma that resulted in intubation / assisted ventilation.

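### Predicting response to ICS is a stated aim, but no planned comparison can separate ICS response from natural course

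*Combined protocol and SAP*

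**What the plan says.** - **Aim.** Sections 2 and 5: the three biomarkers are to predict wheezing attacks "as well as response to treatment with inhaled corticosteroids, as a preliminary to a large, randomised controlled trial". Section 4.2 gives the purpose as picking out the children who will benefit from ICS. The bulleted objectives, however, name only attacks and clinical outcome over one year.
- **Treatment.** Section 6: "All treatment and routine monitoring decisions will be at the discretion of their treating general practitioner (GP) or paediatrician". There is no allocation and no control group.
- **Who is enrolled.** Section 7.2.1 admits children with wheeze diagnosed by a doctor "who has decided to prescribe any bronchodilator, ICS or montelukast on clinical grounds". Children not on ICS can therefore be in the cohort; their expected number is not given.
- **ICS stopping and escalation rule** (sections 2, 6 and 7.1). If ICS is stopped, the reason is recorded as ineffective treatment, or as stopping "if the child was so well that the family or GP did not wish to continue (treatment success or spontaneous improvement". In addition: "If an additional medication is prescribed, or the child is referred to secondary care, this will be considered as treatment failure".
- **Outcomes.** Section 6.1 lists unscheduled visits as primary, with days lost, oral steroid use, rescue use and TRACK as secondary. The stopping and failure classes are not among them.
- **Analysis.** Section 11 lists chi-squared, Fisher, t and Mann-Whitney tests. It specifies no measure of ICS response, no contrast by ICS status, no interaction and no adjustment.
- **Background.** Section 4.3, on the cited three-way crossover study of 300 children: "Sixty improved spontaneously over the duration of the study". Also: "Those with no positive SPTs or elevated eosinophil count rarely had acute attacks of wheeze".

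**The concern.** A marker that predicts response to a drug is one for which the difference between treated and untreated outcome varies with the marker. A marker that predicts outcome whatever the treatment is prognostic. Looking only at ICS users, the two cannot be distinguished. The stopping rule adds to this by giving one class to two opposite explanations. The failure rule has the mirror problem, because escalation or referral may reflect natural severity as well as lack of drug effect. Replacing these classes with attacks or TRACK among ICS users does not help, since the missing element is the comparison with children not on ICS.

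The background gives a reason to expect prognosis to differ by biomarker, with marker-negative children having few attacks. What is at stake is the next step: section 4.3 wants pilot data to inform the power calculation of a randomised trial. A prognostic difference taken for ICS response, or a real response hidden by prognosis, could misdirect that trial's choice of population and effect size.

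**Working it through.** The plan states no power, effect size or event rate, and 100 is a recruitment target, so there is no figure to reproduce. The scenarios below are illustrations.

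**From the documents:** 60/300 = 20% improved spontaneously (section 4.3, not split by biomarker); N = 100 (section 5); significance at p<0.05 (section 11, sidedness not given, two-sided assumed).

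**Assumed:** the biomarker split, the natural rates by biomarker, the ICS effect, the number on ICS, and that every well child on ICS stops it and enters the favourable class.

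**1. A real response can be hidden.** Let s be the natural rate of becoming well and e the share of the remaining positives made well by ICS, with no ICS effect in negatives. The class then holds s₊ + (1 − s₊)e of positives and s₋ of negatives; the true gain in positives is (1 − s₊)e. With e = 0.25:

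| s₊ / s₋ | Positives in class | Negatives in class | Apparent gap | True gain in positives |
|---|---|---|---|---|
| 15% / 25% | 0.15 + 0.85×0.25 = 36.25% | 25% | +11.25 points | 21.25 points |
| 10% / 30% | 0.10 + 0.90×0.25 = 32.5% | 30% | +2.5 points | 22.5 points |
| 0% / 40% | 0 + 1×0.25 = 25% | 40% | −15 points | 25 points |

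Each pair averages 20% at a 50:50 split.

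**2. A false signal can appear.** Set the ICS effect to zero, with natural rates of 10% (positive) and 30% (negative) and a 50:50 split. The chance of p<0.05 is the sum of Bin(a; n₊, 0.10) × Bin(b; n₋, 0.30) over all tables (a, b) that the test calls significant:

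| ICS users | Chi-squared, uncorrected | Fisher |
|---|---|---|
| 50 | 45.0% | 30.5% |
| 70 | 56.5% | 45.5% |
| 100 | 73.4% | 64.0% |

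With 100 users, 15% against 25% gives 24.4% (chi-squared) or 17.2% (Fisher), and 5% against 35% gives about 97% (normal approximation). Equal rates of 20% give 5.2% and 2.8%, so the signal comes wholly from the assumed difference in prognosis. With 30% biomarker-positive and rates of 10% and 30% (average 0.3×10% + 0.7×30% = 24%), the normal approximation gives 30%, 42% and 59% for 50, 70 and 100 users.

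**3. What a reference group would add.** Assume ICS raises the well rate from 10% to 30% in positives, and negatives are at 30% on or off ICS. Users alone show 30% against 30%. The difference between the on-ICS and off-ICS contrasts is (30 − 10) − (30 − 30) = 20 points. Its standard error is √Σ p(1 − p)/n over the four cells:

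- 50% positive, 50% on ICS (25 per cell): √[(0.21 + 0.09 + 0.21 + 0.21)/25] = √0.0288 = 0.170; 95% half-width 1.96 × 0.170 = 33 points; power 22%.
- 30% positive, 70% on ICS (cells of 21, 9, 49, 21): √(0.21/21 + 0.09/9 + 0.21/49 + 0.21/21) = √0.0343 = 0.185; half-width 36 points; power 19%.
- 30% positive with 50% on ICS, and 50% positive with 70% on ICS, both give 35 points and power 20%.

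These half-widths are percentage points for a yes/no outcome, not TRACK units. They allow for chance only, not for doctors choosing who receives ICS.

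**4. Is ICS status recorded?** Appendix 4, Question 4 asks about inhaled and oral corticosteroids in one yes/no item. A No identifies a month without ICS; a Yes does not. The follow-up fields ask dose, frequency and duration but have no place for the drug. A child not on ICS who receives oral steroids for an attack would answer Yes, so the ambiguity falls in months with attacks.

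**The case against.** Several points on the other side are sound.

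- **The plan does not attribute the favourable class to ICS.** A reader might infer that natural recovery in biomarker-negative children will be counted as ICS response. The documents do not support that: the label itself allows for spontaneous improvement, the class is not a listed outcome in section 6.1, and section 11 does not analyse it.
- **Other outcomes exist.** Attacks, TRACK, oral steroid use and rescue use are collected on every child, including those on ICS. This stands, but without a contrast by ICS status they do not separate response from prognosis either.
- **The background evidence is indirect.** The 60 children are not split by biomarker, and the study as described compared active treatments with no untreated arm. It suggests a milder course in marker-negative children but does not measure it.
- **The reversal is a corner case.** A reader might infer that the biomarkers would look inversely predictive of a real response. Under the first model that needs rates such as 0% and 40%, which nothing in the documents supports; the other two scenarios keep the correct sign.
- **This is a feasibility study** that defers the definitive question to a randomised trial, and its objectives omit ICS response. That limits the damage, but the aim sentence still makes the claim.
- **A reference group is no cure.** An on/off-ICS comparison would be confounded by indication and very imprecise. This stands, and is why the first remedy is to narrow the aim.

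**Conclusion.** The point holds in this form: the aim includes something that the design and analysis cannot deliver. Treatment is not allocated, no comparison with children off ICS is planned, and the ICS-specific classes mix drug effect with natural course. A biomarker difference among ICS users, or the absence of one, is uninterpretable as evidence on ICS response.

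The size cannot be derived from the documents. Under the assumed rates, the favourable class could shrink a true 21 to 23 point gain to a gap of 2.5 to 11 points, or give a significant difference with no drug effect in roughly a quarter to three quarters of studies (chi-squared, equal split, across the 15%/25% and 10%/30% scenarios). These figures rest on assumed natural rates by biomarker, an assumed number on ICS, and every well child stopping ICS. The conclusion does not depend on them.

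Prediction of attacks, the prognostic part of the aim, is not affected by this point. The documents do not show that the study will report natural recovery as ICS success or find an inverse relation. The change should be made because it alters what the study may claim, at little cost.

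**What to change.** 1. **Sections 2 and 5.** Limit the aim to predicting attacks (prognosis) and describing outcomes while on ICS. Leave prediction of ICS response to the future randomised trial.
2. **Section 11.** Show the biomarker contrasts in attacks and TRACK side by side by ICS status, with on ICS defined in advance (for example, prescribed ICS at the first study visit). Give the difference between the contrasts with a confidence interval, and label it exploratory, non-randomised, confounded by indication and imprecise: about ±33 to 36 percentage points for a yes/no outcome at N = 100 under the assumptions above. Confirm that the entry data record ICS prescription.
3. **Appendix 4, Question 4.** Ask about inhaled and oral corticosteroids in separate items, so that ICS exposure can be identified month by month.
4. **Sections 2, 6 and 7.1.** State that the stopping and escalation classes are descriptive and will not be used as evidence of ICS response or non-response.

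None of this touches how children are treated. The cost is protocol wording, one questionnaire item and one extra table. The downside is a more modest aim and an exploratory table too imprecise to settle anything. Months already answered on the combined item would stay ambiguous unless ICS use can be confirmed at the three-monthly reviews.

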4.2. RATIONALE FOR CURRENT STUDY

Inhaled corticosteroids are effective treatment at all ages for patients with eosinophil airway disease, but have side-effects, including growth suppression, adrenal failure and increased susceptibility to respiratory infection. Only some children with preschool wheeze have airway eosinophilia, and thus benefit from inhaled corticosteroids, but these cannot be distinguished from the non-eosinophil phenotypes clinically. By using three simple point of care tests (blood eosinophil count, skin prick test to aeroallergens and FeNO) we aim to select out the subgroup of responders who will benefit, while avoiding exposing non-responders to potential side-effects.

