If the child has been prescribed OCS, testing will be delayed by 2 weeks for biomarker testing as soon as the electronic informed consent is submitted. Finally, parents will be informed through the patient information sheet as well as, in person, that a second optional testing will take place 3 months after the first one, in their second study visit. This will allow assessing the reproducibility of the obtained biomarker results, thus additionally assess their stability.

Patient recruitment at a site will only commence once the study team has ensured the following:

- HRA approval
- Completed Local Site Delegation of Duties and Signature Log
- Confirmation of Capacity and Capability

All recruitment procedures will be in accord with the GCP, and parents/carers will be given detailed information regarding the study as well as all the time they need to understand it. Parents/guardians have at least 24 hours to consider participation. Recruitment will only commence after parents/carers have fully understood the project and given informed consent online through the Qualtrics® platform (offered by Imperial College London).

Child participants entering the study upon their parents' wish, will be fully screened by the Principal Investigator (PI) or someone else from the research team who is suitably qualified and delegated to do so, with the latter taking informed consent as well. After the electronic informed consent sheet is submitted, parents will be asked to provide the contact details of their child's GP or paediatrician, to inform him/her about the child's participation in this study through a letter sent by email along with this patient information sheet. In addition, we will ask them to provide some of the child's personal data (Appendix 1: Recruitment Plan, Table 3: The personal data that will be obtained

by each individual participant). Children's full name, date of birth, gender, ethnicity as well as, their parent's full name, telephone number and email address will be added in the child's patient card. All other data obtained from the study will be added in the Case Report Form (CRF).

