Follow-up: We will arrange for a short monthly electronic questionnaire to be sent by email to the parents/carers, in order to record on a monthly basis, the days their child was out of childcare, days the carer missed from work, unscheduled health care visits and use of rescue therapy or oral corticosteroids (including dosage) (Appendix 4: Monthly Questionnaire). In addition, we will record the children's TRACK™ score (Test for Respiratory and Asthma Control in Kids) (Appendix 3: TRACK™ score questionnaire) every 3 months, to assess wheeze control. The questionnaires will be made and sent through the Qualtrics® questionnaire platform (offered by Imperial College London). There will be review visits every 3 months, to evaluate their progression in person, but if not feasible, video calls will be arranged through Microsoft Teams. Correct use of spacers will be ensured after guiding parents on how to use them and will be done by their GP or paediatrician as well as from [name] who is a registered pharmacist in the UK.

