19.4. APPENDIX 4: MONTHLY QUESTIONNAIRE

Introduction: Please take a moment to complete the following questionnaire relating to your child's wheezing condition. The questions will help us identify wheezing exacerbations and assess your child's quality of life.

Question 1: Did your child experience any wheezing symptoms during the last month?

Not at all	Once or twice	Once every week	2 or 3 times a week	4 or more times a week
				

Question 2: Was the child unable to go to childcare because of breathing problems?

Yes	No	N/A
		

If **yes**, please state how many days: _____ (Number)

Question 3: Did you have to take your child for an emergency appointment with your GP, urgent care or hospital because of wheezing?

Not at all	Once or twice	Once every week	2 or 3 times a week	4 or more times a week
				

Question 4: Was your child treated with inhaled or oral corticosteroids?

Yes	No
	

If **yes**, what was the dose, frequency and duration?

Dose:	Frequency:	Duration:
_____	_____	_____

Question 5: Was your child given β 2 agonists (blue inhaler, rescue therapy)?

Yes	No
	

If **yes**, what was the dose, frequency and duration?

Dose:	Frequency:	Duration:
_____	_____	_____

Question 6: Did you have to take days off work because your child had wheezing or breathing difficulties?

Yes	No
	

If **yes**, how many days did you take? Specify number: _____ (days)

Survey's ending message: "We thank you for your time spent taking this survey. Your response has been recorded."

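### Monthly Question 4 merges inhaled and oral steroids although oral steroid use is a listed outcome; second and smaller, the treatment-failure rule leaves ICS dose increases unclassified (minor to moderate)

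*Combined protocol and SAP*

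**What the plan says.** **Oral steroid use.** Section 6.1 lists it as a secondary outcome. The follow-up text in Section 6 says the monthly form will record "use of rescue therapy or oral corticosteroids (including dosage) (Appendix 4: Monthly Questionnaire"). The form is in Appendix 4. Its Question 4 reads "Was your child treated with inhaled or oral corticosteroids", with a single yes/no. If yes, it asks "what was the dose, frequency and duration", with one space for each. There is no field for product, route or reason.

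**ICS response.** The aim in Section 5 includes predicting exacerbations "as well as response to treatment with inhaled corticosteroids, as a preliminary to a large, randomised controlled trial". Section 4.2 puts the purpose as "we aim to select out the subgroup of responders who will benefit". The only explicit classification of ICS response is in the follow-up text, worded alike in Sections 2, 6 and 7.1. ICS stopped as ineffective is a failure. ICS stopped because the child is well is success or spontaneous improvement. Then: "If an additional medication is prescribed, or the child is referred to secondary care, this will be considered as treatment failure".

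**Who prescribes, and what else is recorded.** Section 6 states "All treatment and routine monitoring decisions will be at the discretion of their treating general practitioner (GP) or paediatrician". It also says "All other data obtained from the study will be added in the Case Report Form (CRF"). The CRF itself is not shown.

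**The concern.** The first problem is measurement of a listed outcome. Many enrolled children may be on daily ICS. For them the Question 4 tick is yes every month whether or not an oral course was given, so the tick carries no information on oral use. The analyst must then infer the drug from whatever a parent wrote as dose and duration. If both drugs were used in a month, there is no second row for the other one.

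The second problem is a hole in a definition. Two children can lose control to the same degree. One gets a second drug and is a failure. The other gets a higher dose of the same ICS and receives no label. Because the treating clinician chooses between these steps, the label depends partly on prescribing style and not only on the child's response. At stake is how clearly this pilot can describe ICS response to those who design the later randomised trial.

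**Working it through.** The plan gives no figure to reproduce on this point, so most of the check sets the texts side by side.

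**Step 1. What Question 4 can distinguish in one month.**

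| Steroid use in the month | Question 4 tick | Rows for dose | Oral use (the outcome) |
|---|---|---|---|
| None | No | none needed | No |
| Inhaled only | Yes | one | No |
| Oral only | Yes | one | Yes |
| Both | Yes | one, for two drugs | Yes |

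Three different states give the same tick, and they differ on the outcome.

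**Step 2. How far off the tick could be if read alone.** Inputs: 100 children (Section 5) and 12 monthly forms each (Appendix 2, Table 2), so at most 100 × 12 = 1,200 forms. A child on ICS all year with no oral course ticks yes on 12 of 12 forms, against a true count of 0. With k such children and every form returned, oral use is overstated by 12k child-months. Section 7.2.1 admits children prescribed any bronchodilator, ICS or montelukast, so k may be anything from 0 to 100, and 12k runs from 0 to 1,200. That is the whole possible range, so the documents give no size. The free-text row narrows it by an unknown amount.

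**Step 3. Is there another source for oral use?** TRACK item 5 (Appendix 3) asks about oral steroids alone, over the past 12 months. At the month 3, 6 and 9 rounds it reaches back 12 − 3 = 9, 12 − 6 = 6 and 12 − 9 = 3 months before follow-up began. Only the month 12 round matches the follow-up year. Its printed answers are grades of extent. It can give any or none over the year by recall, but not timing, number of courses or dose.

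**Step 4. What the failure rule classifies.**

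| Event during follow-up | Class in Sections 2, 6 and 7.1 |
|---|---|
| ICS stopped as ineffective | Failure |
| ICS stopped because child is well | Success or spontaneous improvement |
| Medicine added | Failure |
| Referred to secondary care | Failure |
| ICS dose raised for uncontrolled wheeze | None |
| ICS continued unchanged | None |

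The last two rows are clinically different and share the same blank.

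**Step 5. Size of the second gap.** Let N be the children prescribed ICS, f those with a failure event as written, and d those with a dose increase for uncontrolled wheeze and no failure event. The rate as written is f/N. With step-ups included it is (f + d)/N. The difference is d/N, zero or positive. Neither d nor N is in the documents, so no percentage can be given.

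**Step 6. Does a planned analysis use the label?** Section 6.1 does not list treatment failure as an outcome. Section 11 names types of test but no variable for ICS response. Attacks and TRACK are collected whatever the label.

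**The case against.** The strongest reply is that nothing specified depends on the failure label, and d may be zero. That stands, and it is why the second gap is the smaller one.

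Next, leaving dose increases out of failure can be defended. A child who regains control on a higher dose may have been an under-dosed responder. That also stands, and the rule should be kept as written.

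Third, the data may be better than they look. Question 4 does ask about inhaled steroids with dose, reviews take place every 3 months, reasons for stopping ICS are recorded, Section 13.5 provides for access to medical notes, and the unseen CRF may hold ICS dose and reason. Free-text dose and duration may often reveal the route. All of this is fair, and one cannot claim that ICS changes go unrecorded. It does not repair Question 4, which is shown in full and is the named source for oral use. A child on both drugs still has one row.

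A reader might infer that the unlabelled step-ups bias the biomarker results or cost power. The documents do not support that: they specify no comparison of failure rates and give no rate to work from. A reader might also want to define regained control after a step-up from TRACK and unscheduled visits. The instruments cannot carry it. Question 3 gives undated frequency bands. TRACK goes out with the monthly form and is not tied to the review visit. An item 5 score of 0 caps the total at 4 × 20 = 80, while Appendix 3 calls control a score above 80.

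**Conclusion.** The concern holds as minor to moderate. The firmer part is Question 4: as printed, it cannot by itself separate oral from inhaled steroid use, and oral use is a listed secondary outcome drawn from that form. This rests on Appendix 4 being the form in use and on some children taking ICS during follow-up. It does not mean that the outcome is lost, since free text, medical notes and the month 12 TRACK item may recover part of it.

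The lesser part is that an ICS step-up for uncontrolled wheeze has no class in the only explicit ICS-response rule. This rests on the plain meaning of an additional medication, which does not cover more of the same drug. Its size is d/N with both terms unknown. It would be wrong to conclude that step-ups should be counted as failures, or that the primary outcome is affected.

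**What to change.** 1. **Split Question 4** into two items, one for inhaled and one for oral corticosteroids, each with its own yes/no, dose, frequency and duration.
2. **Keep the failure rule** in Sections 2, 6 and 7.1, and add after it text such as: *At each 3-monthly review, any change in ICS dose since the last review will be recorded with its date and reason. Among children prescribed ICS, the treatment-failure rate and its components (ICS stopped as ineffective, medicine added, referral) will be reported, with the number of children whose ICS dose was increased for uncontrolled wheeze shown descriptively beside them.* The new recording is needed only if the CRF does not already hold these items.

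**Cost.** One extra item on at most 1,200 monthly forms, and a dose-change entry at no more than 100 × 4 = 400 reviews, fewer because children not on ICS skip it. Section 17 requires prior Sponsor and HRA review of departures from the protocol, and Section 12.1 says approval has already been obtained, so this is a small amendment. Forms and reviews completed before it would lack the new detail, and the report should say from which date it is available. Clinical care does not change.
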